8.1.2 COHORT EXPANSION

After the dose escalation part is completed, 16 patients will be enrolled into a Dose Expansion Cohort at the MTD of the combination. All patients will enter directly into 21-day combination cycles and will be given NOX66 therapy for 7 days and doxorubicin will be administered on Day 2. This will be followed by a 2-week rest period. Treatments will continue up to 6 cycles.

For both the Dose Escalation and Cohort Expansion groups, treatment will be terminated upon disease progression, unacceptable toxicity or a maximum of 6 cycles. In patients who develop Grade 3 or 4 toxicity determined to be related to NOX66, the Investigator may reduce the dose or frequency of dosing by one level so that the patients can remain in the study. Furthermore, all patients will be actively followed up for about 14 months after completion of Cycle 6 (including scheduled visits every 3 months) followed by telephone follow-up/chart review, for PFS and OS, at 15 and 18 months from the start of Cycle 1.

8.2 STUDY TREATMENTS

Idronoxil is a multiple-signal transduction regulator which results in cell death via extrinsic and intrinsic apoptosis, anti-angiogenesis, and immunomodulation via stimulation of natural killer cell activity. The study drug (NOX66) is formulated in a single use suppository with a proprietary lipophilic base containing 400 or 600 mg of idronoxil. The suppository will be self-administered by each patient according to the dose level assigned.

Doxorubicin is a cytotoxic anthracycline antibiotic that binds to nucleic acids, presumably by specific intercalation of the planar anthracycline nucleus with the DNA double helix. Doxorubicin hydrochloride for Injection, USP, a sterile red-orange lyophilized powder for intravenous use only, is available in 10, 20 and 50 mg single dose vials and a 150 mg multidose vial. It is recommended that doxorubicin be slowly administered into the tubing of a freely running intravenous infusion of Sodium Chloride Injection, USP, or 5% Dextrose Injection, USP. The tubing should be attached to a Butterfly® needle inserted preferably into a large vein. Prior to the start of each cycle, patients must have a minimum ANC of $1000/\mu\text{L}^3$ to reduce the risk of infection from suppository insertion.

8.3 DEFINITION AND DETERMINATION OF MTD AND DLT

8.3.1 DEFINITION OF MTD

The MTD is defined as the maximum dose level at which no more than 1 patient out of 6 experienced a DLT at the end of Cycle 1.

8.3.2 DETERMINATION OF MTD

If at any given dose level, when 1 of 3 patients develops a DLT during Cycle 1, then the dose escalation will halt temporarily, and an additional 3 patients will be recruited at the same dose level. If no further DLTs occur, then dose escalation will resume with the next 3 patients receiving the next higher dose of NOX66. If there are 2 or more patients (out of 6) who

experience DLTs during Cycle 1, dose escalation will be halted, and that level will be declared the DLT dose level. The previous dose level will then be considered for expansion to 6 patients in order to confirm that it is the MTD level. If in the first group at 800 mg, 2 or 3 patients develop DLTs then that dose level is considered to be the DLT level and 3 additional patients need not be tested at that level, but lower doses should be studied.

8.3.3 DEFINITION OF DLT

Any of the following, if judged to be associated with the combination of NOX66 and doxorubicin (i.e., possibly-, probably-, or definitely related), during Cycle 1, at each dose level, will be considered a DLT using the NCI-CTCAE Version 5.0:

- 1) Grade 3 non-hematological toxicities (excluding alopecia) with the following exceptions:
 - i. Grade 3 nausea/vomiting or diarrhea <72 hours with adequate antiemetic and other supportive care
 - ii. Grade 3 fatigue <1 week
 - iii. Grade 3 electrolyte abnormality that lasts 24 to 72 hours (Investigator's discretion for timeframe), is not clinically complicated and resolves spontaneously or responds to conventional medical interventions.
- 2) Grade 4 non-hematologic (non-laboratory) toxicity of any duration
- 3) Grade 3 or Grade 4 febrile neutropenia of any duration not caused by doxorubicin. *It is well known that a dose-dependent, reversible leukopenia and/or neutropenia are the predominant manifestations of doxorubicin hematologic toxicity and are the most common acute dose-limiting toxicities of this drug. With the recommended dose schedule, leukopenia is usually transient, reaching its nadir 10 to 14 days after treatment with recovery usually occurring by the 21st day.*
- 4) Grade 3 thrombocytopenia in combination with a Grade 3 or greater blood and lymphatic system disorder, not attributable to doxorubicin
- 5) Grade 3 AST or ALT that is associated with a Grade 2 or greater rise in bilirubin

Based on the limited experience with NOX66 and the known toxicities of doxorubicin, it is possible that there may be overlapping toxicities in terms of anemia, neutropenia, nausea, and asthenia.

If patients develop any DLT during NOX66 monotherapy and/or during Cycles 2 to 6 of the combination, these will be considered "DLT equivalent toxicity" and will be recorded in the eCRF. Growth factor support (except during Cycle 1 in the Dose Escalation Cohorts) or other supportive medication (anti-emetics) at any cycle may be given at the discretion of the Investigator.

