The MTD of the combination of NOX66 and doxorubicin will be determined over the first 21-day interval (Cycle 1) following monotherapy with NOX66 and in combination of doxorubicin-in 1 of 3 consecutive dose cohorts. The MTD of the combination will either be considered one dose level of NOX66 lower than the dose which produces ≥ 2 DLTs in 3 or 6 patients, depending if a DLT occurred in the first 3 patients, or the highest dose level tested (1800 mg daily) if the aforementioned condition does not occur. A DLT will be defined as a protocol-specified adverse event of toxicity Grade 3-4 (National Cancer Institute Common Terminology Criteria for Adverse Events [NCI-CTCAE] V 5.0) which is considered possibly, probably, or definitely related to the combination of NOX66 and doxorubicin (Section 8.3).

Since this is a multicenter trial, the sites are to notify the Sponsor or designee when a patient has been declared eligible to participate. After 3 patients have completed a 21-day treatment cycle of the combination of NOX66 and doxorubicin and all the safety data are available, assessment of toxicities and decisions about dose escalation and cohort expansion (see below) will be made by the SRC, which will include at least one Sponsor representative participating Investigators, and may also include a cardiologist or other external consultants at the Sponsor's discretion. Recommendations from the SRC could include 1) repeat a dose level, 2) await further safety data if follow-up is pending for patient(s) as determined by the Investigator(s), 3) discontinue the study, 4) escalate the dose to next possible level or 5) take other actions.

Three new patients will be entered at the next dose level of NOX66, if there were no DLTs or only 1 of 6 patients had a DLT at the end of the first cycle.

If no DLT is observed at 1800 mg (Cohort 3), dose escalation will be stopped. The proposed highest dose level (1800 mg) will be declared the MTD, and additional patients will be enrolled, if necessary, to ensure that a total of 6 patients are evaluated at this dose level.

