8.3.5 EVALUABLE PATIENT

The criteria for determination of an evaluable patient for a dose escalation decision or determination of MTD, must include:

- Patient who experienced a DLT during the 21-day combination treatment cycle (Cycle 1) or
- Has not experienced a DLT and has taken at least 80% of the prescribed daily doses of NOX66 and completed all safety evaluations required in Cycle 1

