8.3.6 PATIENT REPLACEMENT

The following guidelines will be used to determine when a patient can be replaced

- During the Monotherapy period in the Dose Escalation part of the study, if a patient who is not tolerating the assigned dose of NOX66, may be replaced with another patient, following a joint decision between the Investigator and Medical Monitor. A maximum of 3 replacements is allowed in each dose level in the Monotherapy period.
- If any patient withdraws consent during Monotherapy period or during Cycle 1, he/she will be replaced with another patient.
- If any patient who has not taken at least 80% of the prescribed daily doses of NOX66 during Monotherapy period and Cycle 1, will be replaced with another patient.
- During the Dose Expansion Part, patients who have not completed at least 2 complete cycles of treatment, will be replaced with additional patients, until at least 12 patients have completed 2 cycles.

The recommended phase 2 dose (RP2D) may be defined as the highest dose of the combination administered if no DLTs are observed and the dosage form is acceptable to patients.

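### Read literally, the DLT list omits three kinds of related Cycle 1 event that are worse than ones it counts, so the count that defines the MTD can be too low

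*Combined protocol and SAP*

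**What the plan says.** Section 8.3.3 lists five items. An event judged possibly, probably or definitely related to the combination in Cycle 1 is a DLT if it fits one of them. The synopsis repeats the list.

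- Item 1: "Grade 3 non-hematological toxicities (excluding alopecia) with the following exceptions". The exceptions cover short nausea, vomiting or diarrhea, short fatigue, and short uncomplicated electrolyte changes, all at Grade 3.
- Item 2: "Grade 4 non-hematologic (non-laboratory) toxicity of any duration".
- Item 3: febrile neutropenia of Grade 3 or Grade 4, not caused by doxorubicin.
- Item 4: "Grade 3 thrombocytopenia in combination with a Grade 3 or greater blood and lymphatic system disorder, not attributable to doxorubicin".
- Item 5: "Grade 3 AST or ALT that is associated with a Grade 2 or greater rise in bilirubin".

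Section 8.1.1 summarises this as: "A DLT will be defined as a protocol-specified adverse event of toxicity Grade 3-4". Section 8.3.1 sets the MTD as the highest level at which "no more than 1 patient out of 6 experienced a DLT at the end of Cycle 1". Under Section 8.3.5 a patient without a DLT is evaluable only if he or she "has taken at least 80% of the prescribed daily doses of NOX66 and completed all safety evaluations required in Cycle 1".

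**The concern.** A toxicity rule should be monotone: if an event counts at one grade, a worse form of it should count too. This list is not. A prolonged Grade 3 electrolyte abnormality is a DLT under item 1, while the same abnormality first seen at Grade 4 fits no item.

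The events left out matter to this trial. Section 11.1.2.4 treats greater myelosuppression and unexpectedly high AST, ALT and bilirubin as signs of an additive NOX66 effect. Section 6.1 reports one death in the carboplatin combination study that may have been related to treatment. That is no rate for this trial, but it shows that a related death is conceivable.

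The MTD is a primary objective, and 16 expansion patients are to be treated at it. DLT status also triggers the immediate notice to other sites and, after two DLTs, the suspension of enrolment (Section 15.2.2.3). An unlisted event triggers neither under that text, although serious adverse event reporting within 24 hours still applies.

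**Working it through.** **No figure to reproduce.** The protocol states no DLT rate, target toxicity or operating characteristic. Section 14.1 says the sample sizes have no statistical basis. The check is therefore textual, followed by an illustration.

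**Step 1: test each event against the list.**

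| Related Cycle 1 event | Nearest item | Why it does not fit |
|---|---|---|
| (a) Non-hematologic laboratory toxicity first recorded at Grade 4 | 1, 2 | Item 1 is Grade 3 only; item 2 leaves out laboratory events |
| (a) continued: Grade 4 AST/ALT with Grade 2 or higher bilirubin | 5 | AST/ALT is fixed at Grade 3; only bilirubin carries the open-ended grade |
| (b) Grade 4 platelets with another blood disorder of at least Grade 3, not due to doxorubicin | 4 | Platelets are fixed at Grade 3; only the partner event is open-ended |
| (c) Death with no earlier listed Grade 3 or 4 phase on record | none | No item names Grade 5; Section 8.1.1 stops at Grade 4 |

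Item 1 does reach laboratory events, because its third exception removes only certain Grade 3 electrolyte changes. The reference in Section 8.1.1 is to events that the protocol specifies, so it points back to the list and fills no gap.

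**Step 2: effect on the count.** Take six patients at one level, one with a listed DLT and one with a first-recorded Grade 4 ALT rise and Grade 2 bilirubin. The list gives 1 of 6, which meets the MTD rule. Counting the worse event gives 2 of 6, the DLT level. In the same way 1 of 3 can become 0 of 3. In case (c) the patient may not have completed the Cycle 1 safety evaluations. He or she is then non-evaluable under Section 8.3.5 and drops out of the denominator as well.

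**Step 3: illustration under assumed rates.** Let p be the true rate of toxicity that ought to count, g the share of patients whose only such event falls in a gap, and c = p − g the counted rate. Both p and g are assumptions.

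- Escalation past a level (0/3, or 1/3 then 0/3): (1−c)³ + 3c(1−c)⁵
- Level meets the MTD rule (at most 1 of 6): (1−c)⁶ + 6c(1−c)⁵

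For p = 0.30 and g = 0.02, c = 0.28. Escalation is 0.373 + 0.163 = 0.536, and the MTD rule is met with probability 0.139 + 0.325 = 0.464.

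| p | Escalate, g = 0 / 0.01 / 0.02 | MTD rule met, g = 0 / 0.01 / 0.02 |
|---|---|---|
| 0.25 | 0.600 / 0.622 / 0.643 | 0.534 / 0.558 / 0.582 |
| 0.30 | 0.494 / 0.515 / 0.536 | 0.420 / 0.442 / 0.464 |
| 0.35 | 0.396 / 0.415 / 0.434 | 0.319 / 0.338 / 0.358 |

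Dropping events can only turn a fail into a pass, so each difference from g = 0 (0.019 to 0.048) is the probability that the decision is reversed.

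**Step 4: sensitivity at p = 0.30.** With g = 0.001 or 0.005 the changes are about 0.002 or 0.010. If every gap patient is replaced instead of being counted as a non-DLT, c = (p−g)/(1−g), and the change in the MTD probability for g of 0.01-0.02 falls from 0.022-0.044 to 0.015-0.031.

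**The case against.** **The gaps are narrower than they first look.** A reader might infer that every Grade 4 laboratory event and every Grade 5 event is missed. The documents do not support that. Nothing says that only the worst grade is tested against the list, so a patient with a documented listed Grade 3 or 4 phase before worsening already has a DLT and is evaluable. Grade 4 AST/ALT is a case of the laboratory gap, not a further gap. The platelet gap needs a second blood disorder of at least Grade 3 and non-attribution to doxorubicin. All this stands. What remains is events whose milder phase is not on record, which can happen because Cycle 1 laboratory tests after Day 1 are scheduled only for Days 9 and 16.

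**Some Grade 4 laboratory exclusion looks intended.** The parenthesis in item 2 is explicit, and the panel in Table 3 includes GGT, triglycerides and uric acid. This too stands: which laboratory values count is the sponsor's choice. It does not explain a scope that counts such values at Grade 3 but not at Grade 4.

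**The committee can act.** It may repeat a level, wait, stop or take other actions (Section 8.1.1). It adjudicates the MTD (Section 15.2.1) and reviews events that are not DLTs (Section 15.2.2.3). A reader might therefore infer either that unsafe escalation will follow or that the gap is harmless; neither is established. The committee can decline to escalate without counting an unlisted event, but Section 5.4 gives its DLT task as applying the definition. Its charter was still to be written and may say more.

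**The 80% dosing rule is a separate matter.** Section 8.3.6 says that a patient "who has not taken at least 80% of the prescribed daily doses of NOX66 during Monotherapy period and Cycle 1, will be replaced", whereas the synopsis and Sections 11.2.2 and 15.2.2.3 describe Cycle 1 replacement for non-safety reasons or noncompliance. A reader might infer that patients who stop for toxicity vanish from the count. Those who stop with a listed DLT do not, because Section 8.3.5 makes them evaluable. Only those who stop for lesser toxicity are unclear.

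**Conclusion.** The point holds as a defect of wording in a rule that sets a primary result. On a literal reading three kinds of related event, (a) to (c) above, are worse than events that count and yet do not count. The direction is certain: each omission can only lower the DLT count. The size is not. The figure of about 2-5 reversals per 100 rests on an assumed 1-2% gap-only rate, true rates of 25-35%, gap patients treated as evaluable non-DLTs, and no committee correction. It is an illustration, and smaller assumed rates give proportionately smaller effects. The likely cause is a drafting slip that the committee would often catch, but the rule should not depend on an override. It should be fixed. Confidence is high for the wording and low for any numerical effect on the MTD.

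**What to change.** Amend Section 8.3.3 and use the same text in the synopsis:

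- Item 1: *Grade 3 or greater*, with exceptions i-iii limited to Grade 3.
- Item 1 or 2: list any Grade 4 laboratory values that the sponsor means to exclude (for example asymptomatic GGT, triglycerides or uric acid), so that none counts at Grade 3 but not at Grade 4.
- Item 4: *Grade 3 or greater* for thrombocytopenia.
- Item 5: *Grade 3 or greater* for AST or ALT.
- Add: *any related Grade 5 event in Cycle 1 is a DLT*. This also makes that patient evaluable under Section 8.3.5.
- Section 8.1.1: replace the Grade 3-4 range with *Grade 3 or greater*.

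As a minor separate item, align the 80% wording in Section 8.3.6 with the other replacement texts.

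The cost is a protocol amendment signed by the sponsor and investigators and submitted to each IRB (Section 17.7), with no new visits or data. The DLT count may be higher, and a lower MTD may be declared.

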8.3.4 DETERMINATION OF DLT

At the end of Cycle 1, all patients in each cohort will be evaluated for DLTs for dose escalation of the next cohort. During the other cycles, assessment of DLTs will be done on an ongoing basis, and if they arise, the doses of NOX66 or doxorubicin or both may be reduced. If a new DLT is most likely related to doxorubicin, the dose of doxorubicin should be reduced to 60 mg/m² or to 37.5 or 18.75 mg.m² (based on serum bilirubin) or delayed until toxicity has been resolved or improved. If the DLT is likely related to NOX66, the Investigator may lower the NOX66 dose and/or extend the dosing interval.

8.3.5 EVALUABLE PATIENT

The criteria for determination of an evaluable patient for a dose escalation decision or determination of MTD, must include:

- Patient who experienced a DLT during the 21-day combination treatment cycle (Cycle 1) or
- Has not experienced a DLT and has taken at least 80% of the prescribed daily doses of NOX66 and completed all safety evaluations required in Cycle 1

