Study Design:	
This is a Phase I, open-label, study of NOX66, given rectally in cohorts of patients with metastatic soft tissue sarcoma who have not been exposed to anthracycline therapy, using a fixed dose-escalation schema every 21 days to establish the MTD. In previous clinical trials, NOX66 has been administered to 18 cancer patients from 400 to 800 mg daily for 14 days prior to combination with carboplatin. In another study 25 patients received up to 16 days of 400 to 1200 mg/day while undergoing radiotherapy. Overall, NOX66 has been well tolerated.
 
Dose-Escalation
 
For all dose escalation cohorts, there will be 7 days of monotherapy treatment with NOX66 followed by a 5- day washout period prior to the start of combination cycles of NOX66 and doxorubicin. The purpose of the monotherapy treatment is to evaluate the safety and tolerability of NOX66 when administered alone and as well as single and multiple dose PK of idronoxil.
 
The study will include three planned Treatment Groups (800, 1200, and 1800 mg daily) of 3 patients each. The first 3 patients will be entered at Dose Level 1 and will be given NOX66 (800 mg daily dose for 7 days) which will be followed by a washout period of 5 days. On Day 1 patients will be monitored for cardiac effects with 12-lead electrocardiograms (ECG) over 8 hours and PK samples will be collected for 24 hours. Patients will be closely monitored for any AEs during monotherapy. If no significant toxicities (defined below) are observed after 7 days of monotherapy and following a 5-day rest period, patients will enter combination therapy. This will commence with Cycle 1, which will consist of 7 days of NOX66 at 800 mg/day and on Day 2 of the 21-day cycle, doxorubicin will be administered at approximately 1 hour after application of NOX66. After a rest period of 2 weeks, Cycle 2 will be initiated with another 7 days of NOX66 treatment at the same dose (800 mg/day) and another dose of doxorubicin on Day 2. Patients will continue to be treated for up to 6 x 21-day cycles of NOX66 and doxorubicin in the same manner.
 
Three new patients will be entered at the next dose level of NOX66, if no dose-limiting toxicities (DLTs) have occurred at the end of Cycle 1.
 
In all cohorts, doxorubicin will be given initially at 75 mg/m^2 as an intravenous infusion over 15 minutes (or as per standard of care). This dose may be reduced to 60 mg/m^2, at the Investigator's discretion for unacceptable Grade ≥ 2 toxicity. Lower doses of doxorubicin (50% or 75% reduction) will be used if serum bilirubin is $1.2 - 3.0 \text{ mg/dL}$ or $3.1 - 5.0 \text{ mg/dL}$ prior to a cycle, respectively.
 
Assessment of MTD
 
At any given dose level, if 1 of 3 patients develops a DLT during Cycle 1, then dose escalation will halt temporarily, and an additional 3 patients will be enrolled at the same dose level. If no further DLTs occur, then dose escalation will resume.
 
If 2 or more patients at a given dose level experience DLTs during Cycle 1, dose escalation will be halted, and that level will be declared the DLT dose

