7 STUDY OBJECTIVES

7.1 PRIMARY OBJECTIVES

- To estimate the maximum tolerated dose (MTD) of NOX66 in combination with doxorubicin
- To characterize the safety and tolerability of NOX66 alone and in combination with doxorubicin.

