8.1.1 DOSE-ESCALATION

For all dose escalation cohorts, there will be 7 days of monotherapy treatment with NOX66 followed by a 5- day washout period prior to the start of combination cycles of NOX66 and doxorubicin. The purpose of the monotherapy treatment is to evaluate the safety and tolerability of NOX66 when administered alone and as well as single and multiple dose PK of idronoxil.

The dose-escalation part of the study will include three planned Treatment Groups (800, 1200, 1800 mg daily) of 3 patients each. The first 3 patients will be entered at Dose Level 1 and will receive daily doses of NOX66 for 7 days. All of these doses, except for the 1800 mg have been evaluated in 2 previous clinical trials and have been relatively well tolerated as monotherapy for 14 days and in combination with carboplatin for 42 days.

After a rest period of 5 days and if no significant toxicities (DLT equivalent toxicity) have occurred, patients will enter the combination therapy part of the study which will consist of up to 6 x 21-day treatment cycles. Each cycle will consist of 7 days of NOX66 (at the assigned dose), doxorubicin (75 mg/m²) on Day 2 of the 21-day cycle (administered at approximately 1 hour after rectal application of NOX66) and a rest period of 2 weeks.

For the 800 mg and 1200 mg dose levels NOX66 will be administered twice-daily (BID) with a 400 mg or 600 mg suppository, respectively, and the 1800 mg dose level will entail administration of a 600 mg suppository three times daily (TID). In all cohorts, doxorubicin will be given initially at 75 mg/m² as an intravenous infusion over 15 minutes (or as per standard of care). This dose may be reduced to 60 mg/m², at the Investigator's discretion for unacceptable Grade ≥ 2 toxicity. A dose reduction of 50% is recommended if serum bilirubin is 1.2 -3.0 mg/dL prior to a cycle. If serum bilirubin is 3.1-5.0 mg/dL prior to a cycle, a 75% dose reduction of doxorubicin is recommended.

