9.2 INCLUSION CRITERIA

Patients must satisfy all of the following criteria to be included in the study:

1. Adult patients (≥ 18 years of age, inclusive at the time of signing the informed consent) with histologically confirmed diagnosis of metastatic or recurrent STS (histopathology, i.e., type of sarcoma and grade needs to be recorded).
2. Patients for whom treatment with doxorubicin is considered to be appropriate (hemoglobin > 10 g/dL, ANC $> 1000/\mu\text{L}^3$, and platelets $> 100,000/\mu\text{L}^3$), serum bilirubin $< 1x$ the institutional upper limit of normal (ULN) (unless known Gilbert's disease), AST or ALT $< 3x$ institutional ULN, and creatinine clearance ≥ 50 mL/min as determined by the Cockcroft-Gault equation. The laboratory normal ranges for clinical laboratory tests must be sent to the Sponsor/CRO before the study is initiated at each site.
3. Left ventricular ejection fraction $\geq 50\%$.
4. Disease that is considered measurable according to RECIST v1.1.
5. Eastern Cooperative Oncology Group (ECOG) performance status of 0–2.
6. Anticipated life-expectancy of at least 6 months.
7. For females of reproductive potential the following are considered highly effective acceptable forms of contraception: surgical sterilization (tubal ligation); total abstinence from sexual intercourse with the opposite sex; established hormonal birth control (e.g., oral, transdermal, injection, or implant) plus a barrier method or a double barrier method (intrauterine device, spermicide, or diaphragm plus condom) for at least 1 month prior to screening and agreement to use such a method during study participation and for an additional month after the last dose of NOX66 or 6 months after the last dose of doxorubicin, whichever is longer.
8. For males of reproductive potential: vasectomy or use of highly effective contraception (e.g., condoms, abstinence) during the study and until 3 or 6 months after the last dose of NOX66 or doxorubicin, respectively, whichever is longer.

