11.4.2.4 Clinical Laboratory Tests

Laboratory assessment samples ([Table 3](#)) are to be obtained at designated visits as detailed in the Schedule of Assessments ([Table 4](#)). Clinical laboratory tests (hematology, clinical chemistry, urinalysis) will be assessed after 7 days of NOX66 monotherapy and will be compared to baseline.

Assessments of hematology, clinical chemistry, and urinalysis are to be performed prior to administration of NOX66 on Day 1 of each Cycle. Hematology and clinical chemistry will also be performed on Days 9 and 16 of Cycles 1 to 6, to determine if myelosuppression or other toxicity has occurred with either NOX66 or the combination of NOX66 and doxorubicin. Prior to each treatment cycle, the same clinical laboratory tests are to be repeated to determine if NOX66 can be administered (ANC > 1000/ μ L³), and to determine if the dose of doxorubicin is to be delayed or reduced if a Grade 2 or higher toxicity is present or Grade 1 or higher serum bilirubin levels are present.

Clinical laboratory tests required at Day 1 of Monotherapy and Day 1 of each cycle can be performed 1 day prior to the scheduled visit day.

At screening, renal function will be assessed by the Cockcroft and Gault formula as noted below:

Creatinine clearance (mL/min) = $\{(140 - \text{age}(\text{years}) \times \text{weight}(\text{kg})/(72 \times \text{serum creatinine}(\text{mg/dL})\} \times 0.85$ (if female).

Table 3 Clinical Laboratory Assessments

Hematology	Serum chemistry	Urinalysis (dipstick)
Haematocrit (Hct)	Albumin	pH
Hemoglobin (Hgb)	Alanine aminotransferase (ALT)	Protein
Mean corpuscular hemoglobin (MCH)	Aspartate aminotransferase (AST)	Glucose
Mean corpuscular hemoglobin concentration (MCHC)	Alkaline phosphatase (ALP)	Blood
Mean corpuscular volume (MCV)	Blood Urea Nitrogen (BUN)	Ketone bodies
Red blood cell (RBC) count	Bilirubin (total and direct)	Specific gravity
White blood cell (WBC) count with differential	Carbon dioxide (CO ₂)	Urobilinogen
Platelet count	Creatinine	Microscopy if needed based on dipstick result
	Sodium	
	Potassium	
	Chloride	
	Calcium	
	Phosphate	
	Magnesium	
	Gamma--glutamyl transpeptidase (GGT)	
	Glucose	
	Lactate dehydrogenase (LDH)	
	Total cholesterol	
	Total protein	
	Triglycerides	
	Uric acid	
Coagulation (Screening Only)		Pregnancy Tests
Prothrombin time (PT)/INR		Urine human chorionic gonadotropin
Activated partial thromboplastin time (PTT)		

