15.2.2.3 Safety Pause and Prompt AE Review

If a DLT occurs in 1 patient in a cohort of 3 patients at a given dose level of NOX66 + doxorubicin, then 3 more patients should be enrolled at that same dose level. If a DLT is not observed in the additional 3 patients, the next cohort of 3 new patients may be enrolled at the next higher dose level.

If DLT occurs in 2 patients in a cohort of 6 patients at a given dose level, then this dose level will be defined as the DLT dose level. All Investigators will be informed, no additional patient(s) will be enrolled at the DLT dose level, and dose-escalation will stop. No more than 6 patients should be enrolled at the DLT dose level.

The dose for the next cohort will be determined at the SRC review meeting to evaluate all the available safety (including AEs that are not DLTs).

When a DLT occurs, the site must immediately inform the CRO who will then inform the other sites that a DLT has occurred and evaluate if a second DLT has occurred at any other sites. If 2 or more DLTs occur at the same dose level, further enrollment of new patients at that dose level or higher across all sites will be suspended until the SRC meeting occurs to evaluate if the MTD has been exceeded. To be included in a dose-escalation decision or determination of MTD, an evaluable patient is defined as one who either experienced a DLT during the first 21-day treatment cycle (Cycle 1) or has not experienced a DLT and has taken at least 80% of the prescribed daily doses of NOX66 of the monotherapy period and the first 21-day treatment cycle and completed all safety evaluations required in Cycle 1.

Due to the potential for Cycle 1 discontinuations, patients withdrawing for reasons other than safety will be replaced.

When a dose escalation is stopped, the patients treated at lower doses can continue as planned.

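### The rule for who counts as DLT-free and evaluable sets no condition on Cycle 1 doxorubicin, so a patient given half the starting dose can count fully toward the MTD of the combination

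*Combined protocol and SAP*

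**What the plan says.** The first primary objective (Section 7.1) is "To estimate the maximum tolerated dose (MTD) of NOX66 in combination with doxorubicin". Section 8.1.1 fixes the partner drug: "In all cohorts, doxorubicin will be given initially at" 75 mg/m².

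A patient without a DLT counts for escalation and the MTD under Section 8.3.5 if he or she "has taken at least 80% of the prescribed daily doses of NOX66 and completed all safety evaluations required in Cycle 1". Section 15.2.2.3 restates this as a patient who "has taken at least 80% of the prescribed daily doses of NOX66 of the monotherapy period and the first 21-day treatment cycle" and completed the Cycle 1 safety evaluations. Section 8.3.6 replaces any patient "who has not taken at least 80% of the prescribed daily doses of NOX66 during Monotherapy period and Cycle 1". None of the three mentions doxorubicin.

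Doxorubicin may nevertheless be lower in Cycle 1. The synopsis says: "Lower doses of doxorubicin (50% or 75% reduction) will be used if serum bilirubin is" 1.2–3.0 or 3.1–5.0 mg/dL before a cycle, respectively. Sections 8.1.1 and 10.2.3 recommend the same cuts. Section 11.4.2.4 repeats the laboratory tests before each cycle, in part "to determine if the dose of doxorubicin is to be delayed or reduced if a Grade 2 or higher toxicity is present or" bilirubin is Grade 1 or higher. Section 9.2 requires bilirubin below 1x "the institutional upper limit of normal (ULN) (unless known" Gilbert's disease), and Section 9.3 makes the same exception.

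**The concern.** A DLT-free outcome informs the MTD of a combination only if the patient received the combination. The evaluability rule guards against under-treatment with NOX66 but not with doxorubicin.

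If the gap operates, it operates in the unsafe direction. A patient whose bilirubin rose during the lead-in would get less doxorubicin in the DLT window, would probably be less likely to have a DLT, and would still be scored as a full tolerated exposure. The 16 expansion patients then enter combination cycles directly at the declared MTD (Section 8.1.2), with doxorubicin planned at 75 mg/m² (Section 11.3, Table 2). With 3 or 6 patients per level, one such patient can change a decision.

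**Working it through.** **1. The plan's reduced doses.** 75 × (1 − 0.50) = 37.5 mg/m² and 75 × (1 − 0.75) = 18.75 mg/m². Both match Section 8.3.4.

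**2. Does any other wording require doxorubicin?** Section 14.1 asks for 80% of prescribed doses without naming the drug, and Section 15.2.2.1 for 80% of the target number. A cycle has 7 × 2 = 14 NOX66 doses (BID) or 7 × 3 = 21 (TID), plus one doxorubicin dose. Even if both drugs are counted, a patient with all NOX66 and no doxorubicin scores 14/15 = 93.3% or 21/22 = 95.5%. A reduced dose is also itself the prescribed dose. Section 8.1.1 convenes the committee after three patients complete a cycle of the combination, but states no doxorubicin amount.

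**3. Which routes to reduced Cycle 1 doxorubicin are open?** Between lead-in and Cycle 1, only DLT-equivalent toxicity stops a patient (Section 8.1.1).

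- *Half dose (bilirubin 1.2–3.0 mg/dL).* Under Section 8.3.3, a bilirubin rise counts if it is itself a Grade 3 or worse non-hematological toxicity, or if it is Grade 2 or higher together with Grade 3 AST or ALT. An isolated lower-grade rise is neither. The documents give no grade cut-off. Assuming Grade 3 begins above 3 × ULN, with ULN 1.0–1.3 mg/dL, the cut-off is 3.0–3.9 mg/dL, so the whole band passes. Known Gilbert's disease at entry is a second way in. This route is open.
- *Quarter dose (3.1–5.0 mg/dL).* On the same assumption the gate stops lead-in rises above 3.0–3.9 mg/dL. That closes all of the band or leaves its lower part. Gilbert's disease leaves a further narrow path.
- *No doxorubicin.* An ANC below 1,000 delays the whole cycle (Section 10.2.3), so it does not produce a NOX66-only Cycle 1. What remains is doxorubicin discontinued, for example after an LVEF fall, with NOX66 continued by agreement with the Medical Monitor (Section 10.2.3).
- *Reduction for Grade 2 toxicity.* Section 10.2.3 ties the cut from 75 to 60 mg/m² to doxorubicin-related toxicity, which cannot exist before the first dose. Sections 8.1.1 and 11.4.2.4 state no cause. The passages conflict.

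**4. Illustrative size.** The documents give no DLT rates, so all risks here are assumptions. Let p be the risk at full doxorubicin and q the risk in one under-exposed patient among six, patients independent:

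P(≤1 DLT in 6) = (1−p)^5 + (1−q) × 5p(1−p)^4

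For p = 0.30 this is 0.16807 + (1−q) × 0.36015. For p = 0.40 it is 0.07776 + (1−q) × 0.2592.

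| p | all six at full dose (q = p) | one at q = 0.10 | one at q = 0.05 |
|---|---|---|---|
| 0.30 | 0.420 | 0.492 | 0.510 |
| 0.40 | 0.233 | 0.311 | 0.324 |

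With two under-exposed patients the ranges are 0.57–0.61 (p = 0.30) and 0.41–0.44 (p = 0.40). With a milder contrast, p = 0.30 and q = 0.20, one such patient gives 0.16807 + 0.80 × 0.36015 = 0.456.

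For the first three patients at p = 0.30, P(0 of 3) goes from 0.7³ = 0.343 to 0.9 × 0.7² = 0.441 with one patient at q = 0.10.

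**The case against.** The strongest points on the other side are these.

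- *The definition may not be exhaustive.* Section 8.3.5 says the criteria must include these items. The committee reviews all data (Section 15.2.2.1), can repeat a level (Section 8.1.1), and will have a charter that is not part of these documents (Section 15.2.1). It could therefore discount an under-exposed patient. But this is discretion: nothing directs it to Cycle 1 doxorubicin, and the exposure summary in Section 14.3.3 lists final doses, cumulative doses and numbers of changes, not the Cycle 1 dose.
- *The Cycle 1 visit list schedules 75 mg/m².* So do the lists for Cycles 2 to 6, where reductions plainly apply, and Table 4, footnote 13, allows a reduced dose in each cycle. The visit list does not exempt Cycle 1.
- *The size is assumed.* This stands. DLT items 3 and 4 exclude febrile neutropenia caused by doxorubicin and thrombocytopenia events attributable to it, so DLT risk may depend less on doxorubicin than a fall from 30% to 5–10% implies.
- *Replacement can itself select.* Removing patients whose lead-in toxicity led to a reduction favors those who tolerated NOX66. This stands, and the fix has to answer it.

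A reader might infer that the MTD could readily rest on patients given a quarter of the dose or none. The documents do not support that: the DLT-equivalent gate largely closes the quarter-dose route for lead-in toxicity, and the no-doxorubicin route needs a discontinuation plus Medical Monitor agreement. Nor do they show that NOX66 lead-in toxicity will in fact lower doxorubicin. The earlier experience described in Section 6.1 reports no bilirubin elevation.

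**Conclusion.** The point holds as a fault in a stated rule. Followed as written, Sections 8.3.5, 8.3.6 and 15.2.2.3 count a patient on half-dose doxorubicin as a full DLT-free observation for a combination MTD, and no other section prevents it. The half-dose route carries the finding.

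If it occurs, the error makes a NOX66 level look safer than it is. On the assumed risks, one under-exposed patient in six adds about 7 to 9 percentage points to the chance of at most one DLT (42% to 49–51%), or about 4 points with the milder contrast (42% to 46%). Its frequency is unknown and may be low. The correction is worth making because it bears on the primary objective, the cohorts are very small, and the cost is slight.

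**What to change.** 1. State in Sections 8.3.5 and 15.2.2.3 that a DLT-free patient is evaluable for escalation and the MTD only if a pre-specified Cycle 1 doxorubicin exposure was received, with the threshold set by the sponsor. Otherwise the patient is replaced for that decision and kept in the Safety Set. Align Sections 8.3.6, 14.1 and 15.2.2.1.
2. Count every DLT, whatever doxorubicin dose was given.
3. Show the Safety Review Committee each patient's Cycle 1 doxorubicin dose beside the DLT outcome, and list every replaced patient with any lead-in toxicity that led to the reduction. Replacement then cannot hide NOX66 toxicity.
4. Reconcile Sections 8.1.1, 10.2.3 and 11.4.2.4 on whether Grade 2 toxicity not related to doxorubicin can reduce the Cycle 1 dose.

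This defines the evaluable set and proposes no dosing rule. The cost is a few sentences and an occasional replacement patient. Section 12.1 allots nine patient numbers per cohort, which is six patients plus the three monotherapy replacements that Section 8.3.6 allows, so a few more numbers may be needed. Some selection toward patients who tolerated the lead-in remains; item 3 makes it visible.
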